5.4.2 Dose-Determination Phase Segment 2 (Double-Blind)

In Segment 2, all patients will start treatment with CORT125281 240 mg QD on Cycle 1 Day 1. Patients will continue on their current dose of enzalutamide during the Screening Period and at the initiation of CORT125281. Beginning on Cycle 1 Day 16, the dose of the investigational agent will be increased in 40-mg increments every 2 weeks, as tolerated, with either CORT125281 (Arm A; N=12) to a maximum dose of CORT125281 320 mg QD or with placebo (Arm B; N=4) (Table 8). If any planned dose escalation is postponed due to transient intolerable Grade 2 toxicity or scheduling conflicts (delays not due to toxicity), the dose may be escalated within 14 days of the planned escalation.

- Arm A (N=12): CORT125281 240 mg QD under fed conditions with upward dose titration in combination with enzalutamide. CORT125281 will be increased in 40-mg increments every 2 weeks (+14-day window) based upon tolerability to a maximum dose of 320 mg QD (Table 8).
 - Cycle 1 Day 1: CORT125281 240 mg QD
 - Cycle 1 Day 16 (+14-day window): CORT125281 280 mg QD
 - Cycle 2 Day 2 to Cycle 2 Day 16 (+14-day window): CORT125281 320 mg QD

- Arm B (N=4): CORT125281 240 mg QD under fed conditions, with an increase in the number of placebo capsules every 2 weeks (+14-day window) (Table 8).
 - Cycle 1 Day 1: CORT125281 240 mg QD
 - Cycle 1 Day 16 (+14-day window): CORT125281 240 mg QD
 - Cycle 2 Day 2 to Cycle 2 Day 16 (+14-day window): CORT125281 240 mg QD

Table 8 CORT125281 Upward Dose Titration for Dose-Determination Phase Segment 2

Dose Level	Resulting CORT125281 Dosage (QD)		Open-Label Bottle (CORT125281)	Blind-Label Bottle (CORT125281 or Placebo) ^a
	Arm A	Arm B		
1 (Starting Dose)	240 mg	240 mg	6 capsules	0 capsules
+1 (First Increase)	280 mg	240 mg	6 capsules	1 capsule
+2 (Second Increase)	320 mg	240 mg	6 capsules	2 capsules

QD, once daily.

Note: The CORT125281 dose will be escalated in 2-week intervals unless there are intolerable Grade 2 toxicities, dose-limiting toxicities, or Grade 3 or greater toxicities attributed to CORT125281 (Section 5.7).

^a. Note: The blind-label bottle contains blinded capsules (CORT125281 [Arm A] or placebo [Arm B]).

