During the double-blind portion of the Dose-Determination Phase (ie, Segment 2), an unblinded Medical Monitor independent of the study team will provide additional oversight for the study, including review of serious unexpected AEs considered related to either CORT125281 or enzalutamide and DLTs.

The DLT-evaluation period will extend from the first dose of CORT125281 through the completion of Cycle 3. The DLT-Evaluable Population will include all patients in Segment 2 who received at least 1 dose of CORT125281 and fulfilled at least 1 of the following:

- Completed 3 cycles of treatment with CORT125281 + enzalutamide and received at least 75% of the study regimen
- Experience a DLT

Patients who are non-evaluable for DLTs will include the following:

- Received <75% of the study regimen for reasons other than toxicity
- Patients who withdraw from the study prior to completion of Cycle 3 for reasons other than toxicity (eg, lost to follow-up, withdrawal of consent, or disease progression)

Patients who are non-evaluable for DLTs will be allowed to continue in the study and receive CORT125281 in combination with enzalutamide. Patients who are non-evaluable for DLTs may be replaced to allow a sufficient number of patients to evaluate DLTs (Section 9.4.1).

After all patients complete 3 cycles of treatment or discontinue treatment, the data will be unblinded and the DRC will meet to review the safety and available PK and PD data. The DRC will evaluate the frequency of DLTs, the DLT rate (number of DLTs in DLT-evaluable patients per week [7-day period] during the DLT-evaluation period), and overall tolerability in their assessment of the dose titration regimen as the Phase 2 RD.

If the DLT rate for the regimen is $\geq 33\%$, alternative titration schemes may be considered as the regimen for the RD, such as greater time increments between dose escalations or limiting the upper range of the regimen to those dose levels corresponding to a DLT rate of $< 33\%$. Once the DRC has determined the RD, patients assigned to Arm B who have not experienced dose reductions due to toxicity will then escalate the CORT125281 dose per the recommended upward titration regimen.

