5.7.1 CORT125281 Dose Modification or Delay

If a patient experiences a toxicity of Grade 3 or greater, or an intolerable side effect, withhold enzalutamide and CORT125281 dosing for 1 week or until toxicity improves to Grade 1 or less, or to the patient's baseline. If the toxicity is attributed to CORT125281, resume CORT125281 at a reduced dose.

In Dose-Determination Phase Segment 1, the CORT125281 dose will be reduced to the next lower dose level as indicated in [Table 7](#), or at least by 25% if the dose is below Dose Level -1.

In Dose-Determination Phase Segment 2, the CORT125281 dose will be reduced in 40-mg increments from the current dose level, without unblinding the patient's treatment assignment (exceptions noted in [Section 5.12.2.1](#)), by reducing the number of capsules from the open-label bottle (the active drug) by 1 for each dose level as indicated in [Table 9](#). Additional PK assessments will be collected in all patients that have a dose reduction to enable exposure-response evaluation at the lower CORT125281 dose ([Table 21](#)).

Table 9 Dose Reductions of CORT125281 for Dose-Determination Phase Segment 2

Before Reduction ^a			First Dose Reduction ^b			Second Dose Reduction ^b		
Dose Level	No. of Capsules from Each Bottle		CORT125281 Dose	No. of Capsules from Each Bottle		CORT125281 Dose	No. of Capsules from Each Bottle	
	Open-Label	Blind-Label		Open-Label	Blind-Label		Open-Label	Blind-Label
+2	6 caps	2 caps	Prior dose – 40 mg	5 caps	2 caps	Prior dose – 40 mg	4 caps	2 caps
+1	6 caps	1 cap	Prior dose – 40 mg	5 caps	1 cap	Prior dose – 40 mg	4 caps	1 cap
1c	6 caps	0 cap	Prior dose – 40 mg	5 caps	0 cap	Prior dose – 40 mg	4 caps	0 cap

cap, capsule; No., number.

Note: The open-label bottle contains CORT125281 and blind-label bottle contains blinded capsules (CORT125281 [Arm A] or placebo [Arm B]).

^a. Reduce CORT125281 by 40 mg according to the current dose level.

^b. If a CORT125281 dose reduction is needed, the patient will have additional PK assessments ([Table 21](#)) after 14 days at the lower dose level to enable exposure-response evaluation at lower CORT125281 doses.

Once the dose has been modified for toxicity, re-escalation is not allowed.

If CORT125281 is discontinued, enzalutamide will be continued per the guidance provided in Section 5.7.1.1.

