9.5.4 Analysis of DLTs

To meet the study primary objective of determining the MTD/ biologically active doses of CORT125281 in combination with enzalutamide, the number, percent and duration of DLTs according to the NCI-CTCAE, version 4.03, will be summarized by CORT125281 dose and overall.

The DLT rate per patient-weeks, defined as the number of DLTs normalized to the total duration of exposure (in weeks) to CORT125281 during the DLT-evaluation period for all patients in the same treatment arm, will also be presented.

Analyses of DLTs will be performed in the DLT-Evaluable Population.

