2.3. Phase 1, Dose-Determination Segment 2 (Double-Blind)

Segment 2 of the Dose-Determination Phase is randomized and double blinded for dose titration with respect to exicorilant in combination with enzalutamide. All patients will receive exicorilant at a starting dose of 240 mg once daily (QD) under fed conditions. Approximately 20 patients will be enrolled to achieve 16 DLT-evaluable patients randomized in a 3:1 ratio to receive exicorilant in combination with enzalutamide either with the starting dose of exicorilant 240 mg QD with dose titration to 320 mg QD (N=12; Arm A) or with the starting dose of exicorilant 240 mg QD, without an increase of the active dose (N=4; Arm B). Patients in Arm B will receive placebo capsules, such that the patient, Investigators, and study team are blinded to which dose patients are receiving (ie, 240 mg QD versus 240 mg to 320 mg QD). In Segment 2, all doses of exicorilant should be taken with food.

All patients will start treatment with exicorilant 240 mg QD on Cycle 1 Day 1. Patients will continue on their current dose of enzalutamide during the Screening Period and at the initiation of exicorilant. Beginning on Cycle 1 Day 16, the dose of exicorilant will be increased in 40-mg increments every 2 weeks, as tolerated, with either exicorilant (Arm A; N=12) to a maximum dose of exicorilant 320 mg QD or with placebo (Arm B; N=4) (Table 1). If any planned dose escalation is postponed due to transient intolerable Grade 2 toxicity or scheduling conflicts (delays in escalation

not due to toxicity), the dose may be escalated within 14 days of the planned escalation.

- **Arm A (N=12):** exicorilant 240 mg QD under fed conditions with upward dose titration in combination with enzalutamide. Exicorilant will be increased in 40-mg increments every 2 weeks (+14-day window) based upon tolerability to a maximum dose of 320 mg QD (Table 1).
 - Cycle 1 Day 1: exicorilant 240 mg QD
 - Cycle 1 Day 16 (+14-day window): exicorilant 280 mg QD
 - Cycle 2 Day 2 to Cycle 2 Day 16 (+14-day window): exicorilant 320 mg QD
- **Arm B (N=4):** exicorilant 240 mg QD under fed conditions, with an increase in the number of placebo capsules every 2 weeks (+14-day window) (Table 1).
 - Cycle 1 Day 1: exicorilant 240 mg QD
 - Cycle 1 Day 16 (+14-day window): exicorilant 240 mg QD
 - Cycle 2 Day 2 to Cycle 2 Day 16 (+14-day window): exicorilant 240 mg QD

Table 1: Exicorilant Upward Dose Titration for Dose-Determination Segment 2

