Dose Level	Resulting exicorilant Dosage (QD)		Open-Label Bottle (exicorilant)	Blind-Label Bottle (exicorilant or Placebo) ^a
	Arm A	Arm B		
1 (Starting Dose)	240 mg	240 mg	6 capsules	0 capsules
+1 (First Increase)	280 mg	240 mg	6 capsules	1 capsule
+2 (Second Increase)	320 mg	240 mg	6 capsules	2 capsules

QD, once daily.

Note: The exicorilant dosage will be escalated in 2-week intervals unless there are intolerable Grade 2 toxicities, dose-limiting toxicities, or Grade 3 or greater toxicities attributed to exicorilant (Protocol Section 5.7).

^a Note: The blind-label bottle contains blinded capsules (exicorilant [Arm A] or placebo [Arm B]). During the double-blind portion of the Dose-Determination Phase (ie, Segment 2), an unblinded Medical Monitor independent of the study team will provide additional oversight for the study, including review of serious unexpected adverse events (AEs) considered related to either exicorilant or enzalutamide and DLTs.

After all patients complete 3 cycles of treatment or discontinue treatment, the data will be unblinded and the DRC will meet to review the safety and available PK and PD data. The DRC will evaluate the frequency of DLTs, the DLT rate (the number of DLTs per week [7-day period] during the DLT-evaluation period), and overall tolerability in their assessment of the dose titration regimen as the Phase 2 RP2D. If the DLT rate for the regimen is $\geq 33\%$, alternative titration schemes may be considered as the regimen for the RP2D, such as greater time increments between dose escalations or limiting the upper range of the regimen to those dose levels corresponding to a DLT rate of $< 33\%$. Once the DRC has determined the RP2D,

patients assigned to Arm B who have not experienced dose reductions due to toxicity will have their exicorilant dose escalated per the recommended Phase 2 regimen.

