One patient may experience more than one DLTs during the DLT evaluation period. Maximum Duration of DLTs will be calculated in weeks and is defined as the End Date of DLT – Start Date of DLT for the longest DLT time duration for each subject. Number of patients with at least 1 DLT, number of DLTs, and maximum duration of DLTs will be summarized by study regimen and overall.

DLT rate per patient-week will also be summarized by study arm, study regimen and overall, where the numerator is the number of patients with at least 1 DLT, and the denominator is the sum of patient's treatment duration (in weeks) during the DLT-evaluation period which is calculated as the days of the patients on treatment during the first 12 weeks divided by 7.

Number of patients with at least 1 DLT and number of DLTs will also be summarized by study arm, highest exicorilant dose level received, and overall.

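### The Segment 2 DLT table by highest dose received (SAP 8.8) groups Arm A patients partly by the outcome, so its rows do not estimate DLT risk at a dose; tabulate by dose at DLT onset instead

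*SAP*

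**What the plan says.** SAP 8.8 plans several DLT outputs for Segment 2. The DLT rates are defined by arm and by cumulative regimen (240; 240-280; 240-280-320 mg), over all DLT-evaluable patients, with a further rate per patient-week. A last sentence adds a supplementary table: patients with at least one DLT and "number of DLTs will also be summarized by study arm, highest exicorilant dose level received, and overall". No denominator is given for its rows.

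Two rules decide which row an Arm A patient falls in. The note to Table 8 in Protocol 5.4.2 reads "The CORT125281 dose will be escalated in 2-week intervals unless there are intolerable Grade 2 toxicities, dose-limiting toxicities" (attributed Grade 3 or greater toxicity is also listed), and the note to Table 1 in SAP 2.3 says the same. Protocol 5.7.1 adds: "Once the dose has been modified for toxicity, re-escalation is not allowed".

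Two places call for DLT information by dose. Protocol 9.5.4 says that the number, percent and duration of DLTs "will be summarized by CORT125281 dose and overall". Protocol 5.4.2 lets the DRC consider, if the regimen's DLT rate is 33% or more, "limiting the upper range of the regimen to those dose levels corresponding to a DLT rate of" below 33%.

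**The concern.** A row of this table is meant to describe a dose, but in Arm A the row is fixed partly by whether the patient had a DLT. A patient with a DLT on 240 mg normally stays in the 240 mg row. A patient who tolerates 240 mg leaves it. The lower rows therefore lose most of their DLT-free patients to the 320 mg row. In the other direction, a DLT that begins after a reduction from 320 mg is still charged to 320 mg.

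This is the only Segment 2 DLT table in the SAP broken down by single dose level, and SAP Section 13 lists no departure from Protocol 9.5.4. It would be natural to take it as the by-dose summary and to hold its rows against the 33% threshold. Read that way, it can make the lowest doses look the least tolerable when dose has no effect on toxicity.

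**Working it through.** **Document inputs.** SAP 2.3: "Approximately 20 patients will be enrolled to achieve 16 DLT-evaluable patients randomized in a 3:1 ratio". So Arm A is 16 × 3/4 = 12 and Arm B is 16 × 1/4 = 4, as stated. The DLT-evaluation period is 3 cycles, or 84 days. The first step is "Cycle 1 Day 16 (+14-day window): CORT125281 280 mg QD" and the second is at the earliest on Cycle 2 Day 2 (Day 30). That gives 15, 14 and 55 days at 240, 280 and 320 mg. The plan gives no power or precision figure for the 16 patients, so there is none to reproduce.

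**Assumptions (not in the documents).** The 84-day DLT risk is 20%, with a constant hazard, meaning no dose effect. Either only DLTs stop escalation, or 10% or 20% of DLT-free patients per step are also held for other reasons.

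**Hazard and period risks.** h = −ln(0.80)/84 = 0.002656 per day, or 0.0186 per week. The risk while at a dose for d days is 1 − exp(−hd):
- 240 mg, 15 days: 3.9%
- 280 mg, 14 days: 3.7%
- 320 mg, 55 days: 13.6%

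**Case 1: only DLTs stop escalation.** Expected DLT patients among 12, by highest dose, are 0.47, 0.42 and 1.51 (total 12 × 0.20 = 2.4). The 320 mg row holds 1.51/2.4 = 63% of them. Every patient left in the 240 or 280 mg row has had a DLT, so:
- within-row proportions: 100%, 100% and 13.6%
- chance that at least one lower row is non-empty: 60%
- the same counts over the arm total of 12: 3.9%, 3.5% and 12.6%, with no low-dose excess

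**Case 2: 10% per step also held.**
- 240 mg row: 0.0391 with a DLT before the step, plus 0.9609 × 0.10 = 0.0961 held. Of those held, 1 − exp(−69h) = 16.7% have a DLT later, which adds 0.0161. Row proportion = (0.0391 + 0.0161)/(0.0391 + 0.0961) = 41%.
- 280 mg row: 0.8648 start 280 mg and 0.8648 × 0.0365 = 0.0316 have a DLT before the next step. Of the remaining 0.8332, 0.0833 are held and 13.6% of these (0.0113) have a DLT later. Row proportion = (0.0316 + 0.0113)/(0.0316 + 0.0833) = 37%.
- 320 mg row: 13.6%. It now holds 12 × 0.7499 × 0.1359 = 1.22 of the 2.4 expected DLT patients, or 51%.

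**Case 3: 20% per step held.** The rows read 31%, 27% and 13.6%.

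The chance that at least one lower row reads 33% or more is 60%, 69% and 68% with 0%, 10% and 20% held. These rows are very small: in Case 1 each lower row has an expected size below half a patient.

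**Schedule variant.** SAP 8.7 puts the steps one day earlier (14, 14 and 56 days). The 320 mg row then reads 13.8% instead of 13.6%. The two passages must be reconciled, but the point does not depend on which applies.

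**Check of the fix.** Assign each DLT to the dose at onset and divide by patient-weeks at that dose (25.2, 22.6 and 81.2 in Case 1). The rate is about 0.0186 per patient-week at all three doses, so the artefact disappears. With a 33% overall risk and true hazards in the ratio 1:2:4, the same tabulation gives 0.011, 0.021 and 0.043, so a real gradient is recovered.

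**The case against.** Four objections have force.

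First, the table as written contains counts, not rates, and every alarming percentage above needs a within-row denominator that the SAP does not state. This stands as a limit on the claim. However, Protocol 9.5.4 asks for percent by dose, SAP 7.3 pairs counts with percentages, and the 33% criterion is a proportion. The missing denominator is itself a gap.

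Second, a reader might infer that the lower rows gather most of the DLTs. They do not when only DLTs stop escalation on schedule: 63% fall in the 320 mg row, because 55 of the 84 days are spent there. That share drops to 51% if 10% per step are held for other reasons, and it reverses with long escalation delays. The distortion is in the row proportions.

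Third, the SAP's defined rates do not group by highest dose. The regimen numerators already count DLTs by the dose being taken, and because the regimens are nested, differencing them gives approximately the patients with a first DLT at 280 mg and at 320 mg. This stands, and it means the DRC is not left with this table alone. What differencing does not give is a denominator of patients who started the level, or patient-weeks at the level.

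Fourth, Arm B stays at 240 mg whatever happens, so its row is unselected, though it has only 4 patients.

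**Conclusion.** The defect is real but confined to Arm A of one supplementary table. Highest dose received is partly a consequence of the DLT, so within-row proportions at 240 mg and 280 mg are biased upward. With 12 patients, a 20% risk and no dose effect, they read 100% when non-empty, or about 41% and 37% with 10% per step held, against a true period risk of about 4%. These sizes rest on the assumed risk, the constant hazard, the assumed held fraction and a within-row reading of the table.

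A reader might go further and infer that the Segment 2 dose decision rests on a biased table. The documents do not support that. The trigger in Protocol 5.4.2 is the DLT rate for the regimen, limiting the range is an option and not a requirement, and the DRC also weighs DLT frequency, the weekly rate and overall tolerability. The supported conclusion is narrower: this table should not be used as the by-dose summary under Protocol 9.5.4, nor to judge which dose levels meet the 33% criterion. It is a cheap improvement.

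**What to change.** In SAP 8.8, replace the grouping by highest dose received with grouping by exicorilant dose level at DLT onset. For each level (240, 280 and 320 mg, and any reduced dose) report:
- patients with a DLT starting at that level, over DLT-evaluable patients who started that level
- DLTs per patient-week at that level

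Both are needed. The planned time at 320 mg is more than three times that at either lower dose, so the first measure rises with exposure even when dose has no effect (3.9%, 3.7% and 13.6% above). Keep the arms separate, with Arm B as its own 240 mg row, and state the denominator in the table shell.

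The cost is a wording change and one re-specified table. SAP 8.7 already lists dosing by date of administration and SAP 8.8 already uses DLT start dates, so no new data are needed and no dosing rule changes. Numbers per level will be small, and the table should say so.

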8.9. Multiple Study Centers

Data analyses will be pooled and not controlled for center effect.

8.10. Sample Size Reassessment

Not Applicable.

8.11. Interim Analyses or Timing of Analyses

The DRC consisting of Investigators, the Medical Monitor, a Clinical Pharmacologist, and additional members as appropriate will review the safety, PK, and PD data following the

completion of each cohort during Dose-Determination Phase Segment 1, after all patients have completed 3 cycles of treatment in Dose-Determination Phase Segment 2, and at least every 6 months during the Expansion Phase.

An interim safety analysis will be conducted after a total of 20 patients complete 3 cycles of therapy in the Expansion Phase. If at any time during the Expansion Phase the DLT rate exceeds 33%, the dose will be declared non-feasible, and no additional patients will be enrolled to that dose. A lower dose level may be evaluated, per the recommendation of the DRC.

9. Efficacy Analyses

The recommendations of the PCWG3 will be used to determine disease response for this study. Tumor assessments include ^{99m}Tc -methylene diphosphonate radionucleotide bone scintigraphy and CT of the chest, abdomen, and pelvis. Baseline tumor assessment will be performed within 28 days before the first dose of enzalutamide (for Dose-Determination Phase Segment 1) and/or the first dose of exicorilant (for Dose-Determination Phase Segment 2 and Expansion Phase). Post-baseline tumor assessments will be performed every 8 weeks after the first dose of enzalutamide and/or exicorilant for the first 24 weeks. Thereafter, tumor assessments will occur at intervals of 12 weeks until disease progression. Objective responses will be confirmed no less than 4 weeks after the criteria for response are first met (if possible, 4 – 6 weeks). PSA, alkaline phosphatase (ALP), and lactic dehydrogenase (LDH) will be assessed at the Baseline/Screening Visit and Day 1 of each cycle. The ITT population will be used to address the secondary and exploratory efficacy objectives of the study. Disease response and progression assessed according to RECIST v1.1 by the Investigator will provide the basis for efficacy endpoints.

At all scheduled visits, data recorded for target, non-target, and new lesions, and Investigator response assessment will be presented in by-patient listings. Summary tables and figures will be provided for endpoints as described in the following sections. Response rate endpoints will be summarized by providing the point and interval estimates. Time-to-event variables will be summarized using Kaplan-Meier estimates and plots.

9.1. Secondary Efficacy Endpoints

Objective Response Rate (ORR): Patient listings of tumor response outcomes (CR, PR, non-CR/non-progressive disease, stable disease, progressive disease, unevaluable, or not assessed) at study visits, as well as best overall response per RECIST v1.1, will be presented by treatment regimen dose group and overall for the ITT population. By-group summary tables will include distribution of response outcomes, best overall response derived over all visits, and point estimates with Clopper-Pearson² 95% CIs for ORR, defined as the proportion of patients with an objective tumor response (either PR or CR) in patients with measurable disease, including best radiographic response for soft tissue.

For supportive purposes, best overall response and point estimates with Clopper-Pearson 95% CIs for ORR will also be summarized using confirmed response.

PSA Levels: PSA levels recorded at each visit will be listed. Proportions of patients in the Safety population who experience a 50% or greater reduction in PSA levels at any visit since baseline will be reported with Clopper-Pearson 95% CIs by treatment group and overall. Mean reduction levels will be characterized via summary statistics. Median time from date of first dose of exicorilant to PSA progression (first occurrence of 50% or greater increase in PSA levels), along with 95% CIs will be estimated via Kaplan-Meier method, and also plotted graphically by treatment group. Patients who are alive and progression-free will be censored at the date of their-last PSA evaluation.

In dose escalation and expansion phases separately, best PSA response will be illustrated graphically via waterfall plots. For each patient, the maximum percent change in PSA levels since baseline will be depicted on the response axis, with vertical bars below the baseline representing decline in the blood-based marker.

Symptomatic Skeletal Event (SSE): SSE is defined as symptomatic fracture, radiation or surgery to bone, or spinal cord compression. SSEs include only symptomatic events of clear clinical significance. Kaplan-Meier estimates of median time from date of first dose of exicorilant to the first occurrence of SSE and associated 95% CIs, will be computed by treatment regimen dose group and overall for the Safety population. Patients who are event-free will be censored at the date of their end of study/treatment + 30 days visit. Kaplan-Meier graph of the probability of the event will also be constructed by treatment group.

Radiographic progression-free survival (rPFS): For the Response-Evaluable population, rPFS will be determined from the first dose of study treatment (exicorilant and/or enzalutamide) to the date when the first site of disease is found to progress on CT, MRI, or radionucleotide bone scan per PCWG3, or death, whichever occurs first. Progression will be assessed by the Investigator using RECIST v1.1.

$$\text{rPFS (months)} = (\text{earliest date of progression, death, or censoring} - \text{date of first study treatment} + 1) / 30.4375$$

Patients who do not experience disease progression or death (due to any cause) will be right-censored at the time of the last tumor assessment date. Censoring date will be based on the date patient was last known to be alive and progression-free (i.e., last assessment date) or data analysis cutoff date, whichever occurs first. Censoring rules are summarized in [Table 3](#) below.

Table 3: Censoring Rules for the Primary Analysis of PFS

Censoring Categories	Date of Censoring
Patients who did not have baseline or postbaseline tumor assessments and did not die on or before the data cutoff date	Date of first study treatment

Patients who did not have disease progression as determined by the Investigator and did not die on or before the data cutoff date	Date of the last adequate tumor assessment on or before the data cutoff date
Patients who did not have disease progression as determined by the Investigator on or before initiation of subsequent anticancer therapy for prostate cancer and did not die on or before the data cutoff date	Date of the last adequate tumor assessment on or before initiation of subsequent anticancer therapy and on or before the data cutoff date
Patients who had 2 or more consecutive missed scheduled tumor assessments immediately prior to disease progression	Date of the last adequate tumor assessment without evidence of disease progression before the 2 missed tumor assessments and on or before the data cutoff date
Patients who did not have disease progression as determined by the Investigator and died more than 119 days from most recent tumor assessment.	Date of the last adequate tumor assessment on or before the data cutoff date

Note: If a patient meets the criteria for more than 1 censoring rule, PFS will be censored at the earliest censoring date.

Kaplan-Meier curves will be plotted by treatment regimen dose groups, and the estimate of median rPFS time (months) with 95% CI will be ascertained. For each cohort, progression-free rate at 4, 6, and 12 months will also be summarized.

Duration of response (DOR): Duration of response will be defined for patients in the Response-Evaluable population as the time from the first occurrence of a documented objective tumor response of CR or PR to the time of radiographic progression (per Investigator using RECIST v1.1) or death from any cause on study, whichever occurs first. Patients who have not experienced disease progression or death will be censored at the time of the last tumor assessment date. Date of censoring will be determined according to same rules as described for rPFS endpoint.

$$\text{DOR (months)} = (\text{earliest date of progression, death, or censoring} - \text{date of first documented objective response} + 1) / 30.4375$$

Kaplan-Meier graph will be plotted by treatment group and estimates of median duration with 95% CIs will be obtained for each dose cohort and overall. Patients who do not achieve a tumor response of CR or PR, will be excluded from this analysis.

Clinical progression: For the Response-Evaluable population, clinical disease progression, defined as time from first dose of study treatment (exicorilant and/or enzalutamide) to date of treatment discontinuation due to disease progression, will be estimated via the Kaplan-Meier

method. Patients who are alive and progression-free will be censored at their end of study visit. Median time to progression and associated 95% CIs will be summarized, overall and by treatment group. Kaplan-Meier graph of the probability of the event will also be plotted by treatment group.

Bone disease progression: For the Response-Evaluable population, bone disease progression, defined as time from first dose of study treatment (exicorilant and/or enzalutamide) to first confirmed appearance of at least 2 new bone metastatic lesions, will be estimated via the Kaplan-Meier method. Cases of equivocal progression will be confirmed by a repeat scan 8 weeks later. Patients who are alive and progression-free will be censored at their end of study visit. Median time to progression and associated 95% CIs will be summarized, overall and by treatment group. Kaplan-Meier graph of the probability of the event will also be plotted by treatment group.

Overall survival (OS): Overall survival will be calculated as the time from the first dose of study treatment (exicorilant and/or enzalutamide) to the date of death from any cause. Deaths that occur on or before the data cutoff date will be considered an event. If a patient has not died before the analysis cutoff date, OS will be censored at the date of last contact on or before the data cutoff date. The last contact date will be derived as follows:

Source Data Conditions	Source Data Conditions
Date of randomization	No condition
Last contact date/last date patient known to be alive from Long-Term Follow-Up eCRF	Use if patient status is reported to be alive Do not use if patient status is reported unknown
End of study	Not lost to follow up
Start/end dates of postbaseline antineoplastic therapy	Nonmissing medication/procedure term
Start/end dates from drug administration record	Nonmissing dose. Doses of 0 are allowed.
End of treatment date from the End of Treatment eCRF	No condition
Investigator overall tumor response assessment date	Evaluation is marked as done.
Laboratory/PK collection dates	Sample collection marked as done.
Vital signs date	At least 1 nonmissing parameter value
ECOG performance status date	Nonmissing ECOG performance status
Start/end dates of adverse events	Nonmissing verbatim term
Physical examination	Evaluation is marked as done.
ECG	Evaluation is marked as done.

The OS in months is defined as follows:

$$\text{OS (months)} = (\text{earliest date of death or censoring} - \text{date of first study treatment} + 1) / 30.4375$$

Median, 25th and 75th percentiles of OS, in months, with 95% CIs will be summarized and plotted graphically by treatment arm and overall using the Kaplan-Meier method.

